### **8.1.13. Transthyretin**

Blood for serum TTR levels will be collected at scheduled time points before the administration of patisiran. Serum TTR will be assessed using enzyme linked immunosorbent assay (ELISA).

### **8.1.14. Thyroid-Stimulating Hormone**

Blood for TSH levels will be collected at scheduled visits.

### **8.1.15. Vitamin A**

Blood for serum vitamin A levels will be collected at scheduled visits before the administration of vitamin A supplementation.

### **8.1.16. Anti-Drug Antibodies**

Serum samples for anti-drug antibodies will be collected as specified in [Table 1](#).

### **8.1.17. Blood Sample for Long-term Storage**

To permit exploratory investigations and the application of novel approaches to bioanalysis that may further elucidate the outcomes of this study, or potentially advance understanding of the safety, mechanism of action and/or efficacy of patisiran, blood samples will be collected for long-term storage. These samples will be securely stored in a central biorepository for up to 10 years following the last patient last visit in this clinical study. After 10 years have elapsed, samples will be destroyed.

Details regarding the collection, processing, storage, and shipping of samples will be provided in the Laboratory Manual.

Exploratory analysis of these biospecimens will be performed by Alnylam Pharmaceuticals or its designees.

All study participants will be advised during the informed consent process of these biobanking details and the potential for exploratory investigation of their samples. Those who do not wish to contribute specimens to the biorepository will be asked to sign an “opt out” form. Moreover, patients who subsequently decide to withdraw consent for the utilization of such stored samples

will be able to do so, with the understanding that any data arising from samples already analyzed will be the property of Alnylam Pharmaceuticals.

## 9. ASSESSMENT OF SAFETY

### 9.1. Safety Parameters

All safety assessment measures will be recorded in the patient's medical record and CRF. Refer to [Table 1](#) for the timing of each safety assessment.

#### 9.1.1. Demographic and Medical History

Patient demographic data will be obtained from the parent study.

The Investigator will assess all patients according to the Karnofsky Scale (see [Appendix 1](#)) and the New York Heart Association Classification of Heart Failure (NYHA; see [Appendix 2](#)).

For all patients, a complete medical history will be obtained, including TTR genotype. Any AEs from the parent study that are ongoing on Day 0 will be considered as part of the medical history.

#### 9.1.2. Vital Signs

Vital signs will be measured pre-dose on all dosing days. Vital signs include systolic/diastolic blood pressure, heart rate, respiratory rate, and body temperature, and will be measured in the supine position using an automated instrument after the patient has rested comfortably for 10 minutes. Each patient's blood pressure should be taken using the same arm. Temperature will be recorded in Celsius or Fahrenheit. Heart rate will be counted for a full minute and recorded in beats per minute. Respirations will be counted for a full minute and recorded in breaths per minute.

For the safety of the patient, additional vital signs may be obtained at the discretion of the Investigator.

#### 9.1.3. Weight and Height

Body weight will be measured on all dosing days to inform the next infusion dosing calculation.

The rules for using body weight to calculate dose are described in [Section 6.4.2](#).

Height will be measured only if it was not obtained in the parent study.

#### 9.1.4. Physical Examination

A physical examination will be performed by a physician before dosing at scheduled time points. The physical examinations will include the examination of the following: general appearance; head, ears, eyes, nose, and throat; cardiovascular; dermatologic; abdominal; genito-urinary; lymph nodes; hepatic; musculoskeletal; respiratory; and neurological.

#### 9.1.5. Laboratory Assessments

Blood samples for clinical laboratory testing will be collected before patisiran dosing at the time points listed in [Table 1](#). All samples will be sent to a central laboratory for analysis. Details on sample collection, processing, and shipping will be provided in a Laboratory Manual.

In the event of an unexplained clinically relevant abnormal laboratory test occurring after patisiran administration, the test should be repeated and followed up at the discretion of the Investigator until it has returned to the normal range or stabilized, and/or a diagnosis is made to adequately explain the abnormality.

#### **9.1.5.1. Hematology**

Blood samples will be collected for evaluation of the following hematology parameters:

- Hematocrit
- Hemoglobin
- Red blood cell (RBC) count
- White blood cell (WBC) count
- Mean corpuscular volume
- Mean corpuscular hemoglobin
- Mean corpuscular hemoglobin concentration
- Neutrophils, absolute and %
- Lymphocytes, absolute and %
- Monocytes, absolute and %
- Eosinophils, absolute and %
- Basophils, absolute and %
- Platelet count

#### **9.1.5.2. Blood Chemistry**

Blood samples will be collected for evaluation of the following chemistry parameters:

- Aspartate transaminase (AST)
- Alanine transaminase (ALT)
- Sodium
- Potassium
- Blood urea nitrogen (BUN)
- Creatinine
- Alkaline phosphatase
- Bilirubin (total and direct)
- Glucose
- Phosphate
- Albumin
- Calcium

#### **9.1.5.3. Urinalysis**

Urine samples will be collected for evaluation of the following urinalysis parameters:

- Visual inspection for color and appearance
- pH
- Specific gravity
- Ketones
- Protein
- Glucose
- Leukocytes
- Bilirubin
- Nitrite
- Urobilinogen
- Microscopic inspection of sediment

#### **9.1.5.4. Coagulation**

A sample for INR assessment will be collected.

#### **9.1.5.5. Pregnancy Testing**

A urine-based pregnancy test will be performed on all females of child-bearing potential prior to dosing at all visits, as specified in [Table 1](#). In cases where a positive urine pregnancy test result is observed, a serum pregnancy test will be administered and the dose will be held. No dose will be administered until a negative pregnancy test is observed. Pregnancy test on the Day 0 Visit does not need to be repeated if the patient had a negative pregnancy test (urine or serum) within 14 days of the first dose.

#### **9.1.6. Ophthalmology Examination**

Ophthalmology examinations will include assessment of visual acuity, visual fields, and slit-lamp evaluation. Visual acuity should be evaluated at the beginning of each specified visit in the study (ie, prior to slit-lamp examination). Manifest refraction will be performed at each specified visit before visual acuity testing and will be used to obtain a correction for visual acuity evaluations. Visual acuity testing should be done with best (most recent) correction.

An electroretinogram (ERG) is a test to evaluate the retinal response to light. It is done to determine if there is damage to rods and cones. ERG testing should be performed if visual changes raise the suspicion for this sort of retinal disease and if clinically indicated.

Further details regarding the ophthalmology examinations will be provided in the Study Reference Manual.

#### **9.1.7. Columbia-Suicide Severity Rating Scale**

The Columbia-Suicide Severity Rating Scale (C-SSRS) will be used to assess each patient's mental status as it relates to suicidal ideation and behavior.

### **9.2. Adverse Events and Serious Adverse Events**

#### **9.2.1. Definition of Adverse Events**

##### **9.2.1.1. Adverse Event**

An AE is any untoward medical occurrence in a patient or clinical investigational patient administered a pharmaceutical product and which does not necessarily have a causal relationship with this treatment.

An AE can therefore be any unfavorable and unintended sign (including an abnormal laboratory finding, for example), symptom, or disease temporally associated with the use of a medicinal product, whether or not considered related to the medicinal product.

Disease progression (including worsening of neuropathy impairment) will not be considered an AE.

All IRRs will be recorded as AEs.

### 9.2.1.2. Serious Adverse Event

A serious AE (SAE) is any untoward medical occurrence that at any dose:

- Results in death
- Is life-threatening (an event which places the patient at immediate risk of death from the event as it occurred; it does not include an event that had it occurred in a more severe form might have caused death)
- Requires inpatient hospitalization or prolongation of existing hospitalization
- Results in persistent or significant disability/incapacity
- Is a congenital anomaly or birth defect
- An important medical event that may not be immediately life-threatening or result in death or hospitalization but may jeopardize the patient or may require intervention to prevent one of the other outcomes listed in the definition above (eg, such events include allergic bronchospasm, blood dyscrasias or convulsions, or the development of drug dependency or abuse)

### 9.3. Relationship to Study Drug

Causal relationship assessment to drug treatments is required for purposes of reporting AEs. To promote consistency, the following guidelines should be taken into consideration along with good clinical and scientific judgment when determining the relationship of drug treatments to an AE:

- Definitely Related: A clinical event, including laboratory test abnormality, occurring in a plausible time relationship to the medication administration, and which cannot be explained by concurrent disease or other drugs or chemicals. The response to withdrawal of the drug should be clinically plausible.
- Possibly Related: A clinical event, including laboratory test abnormality, with a reasonable time sequence to the medication administration, but which could also be explained by concurrent disease or other drugs or chemicals. Information on the drug withdrawal may be lacking or unclear.
- Unlikely Related: A clinical event, including laboratory test abnormality, with little or no temporal relationship to medication administration, and which other drugs, chemicals, or underlying disease provide plausible explanations.
- Not Related: A clinical event, including laboratory test abnormality, that has no temporal relationship to the medication or has more likely alternative etiology.

### 9.4. Recording Adverse Events

The patient should be asked about medically relevant changes in his/her health since the last visit. The patient should also be asked if he/she has been hospitalized, had any accidents, used any new medications, or changed concomitant medication routines (both prescription and OTC).

In addition to patient observations, AEs will be documented from any clinically relevant laboratory findings, physical examination findings, or other findings.

Adverse events are to be graded according to the categories detailed below.

Mild: Mild events are those which are easily tolerated with no disruption of normal daily activity.

Moderate: Moderate events are those which cause sufficient discomfort to interfere with daily activity.

Severe: Severe events are those which incapacitate and prevent usual activity.

Changes in severity should be documented in the medical record to allow assessment of the duration of the event at each level of severity. Adverse events characterized as intermittent require documentation of the start and stop of each incidence. When changes in the severity of an AE occur more frequently than once a day, the maximum severity for the experience that day should be noted. If the severity category changes over a number of days, then those changes should be recorded separately (with distinct onset dates).

## 9.5. Reporting Adverse Events

The Investigator is responsible for reporting all AEs that are observed or reported after the first dose of patisiran regardless of their relationship to patisiran administration through the end of the study.

Any medical condition that is present when the patient enters this extension study and does not deteriorate should not be reported as an AE. However, if it does deteriorate at any time during the study, it should be reported as an AE.

All AEs must be fully recorded in the site's source records and in the patients' CRF, whether or not they are considered to be drug-related. Each AE should be described in detail: onset time and date, description of event, severity, relationship to investigational product, action taken, and outcome (including time and date of resolution, if applicable).

Adverse events should be followed through the end of study visit or until recovery to the normal state has been achieved, whichever occurs first. In the event of a patient not returning to the clinical unit, the outcome of this event will be recorded as lost to follow-up.

For patients who withdraw from the study early, ongoing AEs will be followed until resolution or 28 days from last dose, whichever occurs first. SAEs will be followed by the Investigator until satisfactory resolution or the Investigator deems the SAE to be chronic or stable.

### 9.5.1. Serious Adverse Event Reporting

An assessment of the seriousness of each AE will be made by the Investigator. Any AE and laboratory abnormality that meets the above seriousness criteria (Section 9.2.1.2) must be reported immediately to the CRO, always within 24 hours from the time that site personnel first learn of the event. All SAEs must be reported regardless of the relationship to patisiran.

The initial report should include at least the following information:

- Patient's study number

- Description and date of onset of the event
- Criterion for serious
- Preliminary assignment of causality

Serious AE reporting will be via electronic data capture (EDC).

To report the SAE, complete the SAE form electronically in the EDC system for the study. If the event meets serious criteria and it is not possible to access the EDC system, send an email to Medpace Safety at PPD or call the Medpace SAE hotline listed below (country-specific phone number will be provided in the Study Manual), and fax the completed back-up paper SAE form to Medpace (country-specific fax number will be provided in the Study Manual) within 24 hours of awareness. When the form is completed, Medpace Safety personnel will be notified electronically and will retrieve the form. When the EDC system becomes available, the SAE information must be entered into the EDC system within 24 hours of the system becoming available. Medpace Safety personnel will be available for SAE reporting on a 24 hour basis. Incoming reports will be reviewed during normal business hours.

Medpace SAE hotline – USA:

Telephone: PPD ext. PPD or PPD ext. PPD

Facsimile: PPD or PPD

Medpace SAE hotline – Europe:

Telephone: PPD

Facsimile: PPD

Within 24 hours of receipt of follow-up information, the investigator must update the SAE form electronically in the EDC system for the study and submit any supporting documentation (eg, patient discharge summary or autopsy reports) to Medpace Safety personnel via fax or e-mail. If it is not possible to access the EDC system, refer to the procedures outlined above for initial reporting of SAEs.

Appropriate remedial measures should be taken by the Investigator using his/her best medical judgment to treat the SAE. These measures and the patient's response to these measures should be recorded. All SAEs, regardless of causality, will be followed by the Investigator until satisfactory resolution or the Investigator deems the SAE to be chronic or stable. Clinical, laboratory, and diagnostic measures should be employed by the Investigator as needed to adequately determine the etiology of the event.

The Investigator will be responsible for reporting all SAEs to the local IEC or IRB when required by national regulations.

The Sponsor or its representative will be responsible for the reporting of all relevant events to the concerned regulatory authorities according to all applicable regulations.

In Europe, in accordance with the Directive 2001/20/EC, the Competent Authorities and the Ethics Committees in the concerned Member States will be notified of fatal and life-threatening Suspected Unexpected Serious Adverse Reactions (SUSARs) as soon as possible but no later than 7 calendar days after the Sponsor or its representative has first knowledge of the minimum criteria for expedited reporting. Non-fatal and non-life-threatening SUSARs should be reported no later than 15 calendar days after the Sponsor or its representative has first knowledge of them.

The Investigator may be informed by the Sponsor or its representative of SAEs from other Investigators or clinical studies which may have relevance to this clinical study. These SAEs should also be reported promptly to the IEC/IRB that approved the study. All SAE reports should be transmitted to the IEC/IRB with a cover letter or transmittal form, and a copy of that transmittal should be maintained in the Investigator's files and forwarded to the Sponsor as part of the trial master file on study completion.

### **9.5.2. Pregnancy Reporting**

A female patient must have a negative pregnancy test within 14 days before the first dose of patisiran on this study. If a female patient is found to be pregnant during the course of the study or during the first month after receiving the last dose of patisiran, the Investigator should report the pregnancy to the CRO within 24 hours of being notified of the pregnancy. Details of the pregnancy will be recorded on the pregnancy reporting form. Treatment with patisiran will be discontinued in any patient who is found to be pregnant during the study. The patient should receive any necessary counseling regarding the risks of continuing the pregnancy and the possible effects on the fetus.

The pregnancy should be followed by the Investigator until completion. At the completion of the pregnancy, the Investigator will document the outcome of the pregnancy. If the outcome of the pregnancy meets the criteria for an SAE (ie, postpartum complication, spontaneous abortion, stillbirth, neonatal death, or congenital anomaly), then the Investigator should follow the procedures for reporting an SAE outlined above.

Pregnancy occurring in the partner of a patient participating in the study should also be reported to the Investigator, who will then report this to the CRO and follow to outcome as described above.

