The suppression of serum levels of TTR and retinol binding protein (RBP) is expected to result in the lowering of circulating vitamin A levels. Preclinical and clinical data have shown that the lowering of circulating vitamin A associated with suppression of RBP does not result in severe vitamin A deficiency. Furthermore, there are individuals with RBP/TTR mutations who have life-long low levels of circulating vitamin A and are essentially in good health, suggesting that there are compensatory transport mechanisms for vitamin A that are yet undescribed. This has also been confirmed in TTR knockout mice, which do not exhibit any manifestations of vitamin A deficiency, with vitamin A uptake by most tissues continuing in the absence of RBP. Provided there is adequate vitamin A in the diet, tissue stores of vitamin A should not be affected by the lowering of TTR and RBP. However, as the vitamin A content of the diet may vary between different countries and different individuals within a country, all patients on the study will be asked to take a daily supplement containing the recommended daily allowance of vitamin A. Patients should have started vitamin A supplementation by the time they start his/her first dose of patisiran.

- Osteoporosis

Patients with FAP may be at risk for osteoporosis. In addition, as part of the premedication regimen administered prior to patisiran dosing every three weeks, FAP patients participating in this study are given glucocorticoids, a drug known to have the potential to reduce bone

mineralization. If there are no medical contraindications, and per investigator judgment and local standard of care, study participants should, if appropriate, receive therapy for the prevention and early treatment of osteoporosis such as: calcium and vitamin D supplementation, bisphosphonates, calcitonin, parathyroid hormone, estrogen agonist/antagonist or combination therapies.

Further guidance to the investigator can be found in the Investigator's Brochure.

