## 4. SELECTION AND WITHDRAWAL OF PATIENTS

### 4.1. Patient Inclusion Criteria

To be enrolled in the study, patients must meet the following criteria before administration of patisiran on Day 0:

1. Have completed a patisiran study (ie, completed the last efficacy visit in the parent study) and, in the opinion of the investigator, tolerated study drug
2. Be considered fit for the study by the Investigator
3. Have aspartate transaminase (AST) and alanine transaminase (ALT) levels  $\leq 2.5 \times$  the upper limit of normal (ULN), international normalized ratio (INR)  $\leq 2.0$  (patients on anticoagulant therapy with an INR of  $\leq 3.5$  will be allowed)
4. Have a total bilirubin within normal limits. A patient with total bilirubin  $\leq 2 \times$  ULN is eligible if the elevation is secondary to documented Gilbert's syndrome (elevation of unconjugated bilirubin with normal conjugated bilirubin) and the patient has ALT and AST levels within normal ranges.
5. Have a serum creatinine  $\leq 2 \times$  ULN
6. Women of child-bearing potential must have a negative pregnancy test, cannot be breastfeeding, and must be using 2 highly effective methods of contraception prior to dosing in this study and agree to use 2 highly effective methods of contraception throughout study participation and for 75 days after last dose of patisiran in this study. Highly effective methods of birth control are defined in Section 4.4.
7. Males with partners of child-bearing potential must agree to use 1 barrier method (eg, condom) and 1 additional method (eg, spermicide) of contraception throughout study participation and for 75 days after the last dose of patisiran in this study; males must also abstain from sperm donation after the first dose of patisiran through study participation and for 75 days after last dose of patisiran in this study
8. Be willing and able to comply with the protocol-required visit schedule and visit requirements and provide written informed consent

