### 4.4. Pregnancy and Breastfeeding Restrictions / Contraception Requirements

TTR transports vitamin A in plasma; therefore, reductions in circulating vitamin A levels accompany reductions in TTR caused by patisiran. Vitamin A deficiency has known effects on both male and female reproductive performance and embryo/fetal development. It is not known whether decreased levels of vitamin A at efficacious patisiran doses in ATTR patients who are male or who are women of child bearing potential will affect reproduction. Histopathological evaluations of all of the reproductive organs have been conducted in the rat and non-human primate (NHP) toxicology studies including a chronic NHP study in sexually mature animals, where there were no adverse effects in males (including sperm analyses and spermatogenic staging) or females. In a dose range-finding rat embryo/fetal development study

conducted with patisiran, there were no effects on mating, fertility, ovarian or uterine parameters, or fetal development despite reductions (-88% from baseline) in serum vitamin A in the dams dosed with the rat-specific TTR surrogate siRNA.

In this study, women of child-bearing potential must have a negative pregnancy test, cannot be breastfeeding, and must be using 2 highly effective methods of contraception prior to dosing on Day 0, throughout study participation, and for 75 days after last dose of patisiran in this study. Highly effective methods of birth control result in a low failure rate (ie, less than 1% per year). Acceptable forms of effective contraception are defined as follows:

- Hormonal: established use of oral, implantable, injectable, or transdermal hormonal methods of conception
- Placement of an intrauterine device (IUD)
- Placement of an intrauterine system (IUS)
- Mechanical/barrier method of contraception: condom or occlusive cap (diaphragm or cervical/vault cap) in conjunction with spermicide (foam, gel, film, cream or suppository)

Note: Failure rates indicate that, when used alone, the diaphragm and condom are not highly effective forms of contraception. Therefore the use of additional spermicides does confer additional theoretical contraceptive protection. However, spermicides alone are inefficient at preventing pregnancy when the whole ejaculate is spilled. Therefore, spermicides are not a barrier method of contraception and should not be used alone.

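### Section 9.5.2 ties the reporting of a female patient's pregnancy to the study or the first month after the last dose, although contraception runs for 75 days; depending on how the course of the study is read, up to about 40–45 of those days carry no clear reporting duty

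*Protocol*

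**What the plan says.** The text examined is the Brazil version 3.1 protocol. Argentina version 3.1 has the same reporting sentence; its contraception section is not in the part of the document available.

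- **Reporting (Section 9.5.2).** A female patient's pregnancy goes to the CRO within 24 hours of notification if it is found "during the course of the study or during the first month after receiving the last dose of patisiran". The pregnancy is then followed to completion and its outcome documented.
- **Contraception (Section 4.1, criterion 6).** Women of child-bearing potential must "agree to use 2 highly effective methods of contraception throughout study participation and for 75 days after last dose of patisiran in this study". Section 4.4 repeats the period: "throughout study participation, and for 75 days after last dose of patisiran in this study".
- **Last scheduled contact (Table 1).** The End of Study and Early Withdrawal visits, each with a pregnancy test, fall 4 (+1) weeks after the last dose.
- **Testing on treatment (Table 1 and its pregnancy-test footnote; Section 9.1.5.5).** A urine test precedes every dose, and a positive result holds the dose until a test is negative.
- **Reason given (Section 4.4).** "It is not known whether decreased levels of vitamin A at efficacious patisiran doses in ATTR patients" will affect reproduction.

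**The concern.** The protocol treats the 75 days after the last dose as a period in which a woman should not conceive, and calls the reproductive effect of the drug unknown. Its duty to report and follow a pregnancy may nevertheless end less than halfway through that period. A site that learns on day 50 that a former patient is pregnant cannot tell from Section 9.5.2 whether a 24-hour report is due or whether the pregnancy must be followed to its outcome.

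The rule also turns on when the pregnancy is found, not when it was conceived. A conception close to the last dose that is recognised on day 45 can fall outside the window, although it lies nearer to exposure than many cases inside it.

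What is at stake is the completeness of pregnancy-outcome information in a rare disease, where each exposed pregnancy is scarce evidence. No efficacy or safety analysis in the plan depends on it.

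**Working it through.** The protocol gives no figure of its own on this point, so the check is a day count followed by a rough scale.

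**Inputs**
- Contraception period: 75 days after the last dose (Sections 4.1 and 4.4).
- Reporting window: the course of the study, or the first month after the last dose (Section 9.5.2). A month is taken as 30 or 31 days.
- Final visit: day 28 to day 35 (Table 1).
- Failure rate of a highly effective method: below 1% per year (Section 4.4).
- Number of women of child-bearing potential: not given; 20 to 100 is assumed for illustration.

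**Reading A: the course of the study is the patient's own participation**

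Uncovered days = 75 − last covered day.
- Month of 30 days: 75 − 30 = 45 (60.0%).
- Month of 31 days: 75 − 31 = 44 (58.7%).
- Final visit at day 35: 75 − 35 = 40 (53.3%).

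A final visit on day 28 does not close the window, because the first-month limb still runs. Reading a month as exactly four weeks would give 75 − 28 = 47 days; that is not relied on.

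**Reading B: the course of the study is the whole trial**

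Let *d* be the number of days from a patient's last dose to study close. With a 30-day month, uncovered days = 75 − max(*d*, 30), and zero once *d* reaches 75.
- *d* = 30 or less: 45 days.
- *d* = 60: 75 − 60 = 15 days.
- *d* = 75 or more: none.

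Patients who leave while the trial still has 75 days or more to run have no gap.

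**Does another provision fill the gap?**
- Section 9.5 ends adverse event reporting at the end of the study. For early withdrawals, ongoing events are followed to resolution or 28 days after the last dose.
- Section 9.2.1.2 makes a congenital anomaly a serious adverse event. A bad outcome might therefore be reported if the site hears of it, but nothing obliges the site to follow the pregnancy until then.
- The partner-pregnancy sentence in Section 9.5.2 has no end date, but it does not cover female patients.

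**Scale**

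At the 1% per year ceiling for one method, assuming adherence, conceptions falling within the uncovered days of Reading A are:
- 40/365.25 × 1% = 0.110 per 100 women.
- 45/365.25 × 1% = 0.123 per 100 women.
- For 20 women: 0.022 to 0.025. For 100 women: 0.110 to 0.123.

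These figures show the order of magnitude only. They apply a conception rate to a window defined by discovery. They leave out pregnancies conceived before the window closes and found afterwards, and they count some conceived late in the 75 days that would not be found until after day 75. They are not an upper bound on what Section 9.5.2 misses.

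**The case against.** **The gap rests on one reading.** On Reading A, with the final visit attended, the first-month limb adds at most 31 − 28 = 3 days, which makes it nearly redundant. Reading B gives it real work after study close. Section 5.2 also refers expressly to the end of the patient's participation when that is what it means. This stands as a reason not to state the 40–45 days without a condition. It does not settle the matter. Section 9.5.2 itself says treatment is discontinued in a patient found pregnant during the study, which fits only someone still being dosed. The month limb also has a use on Reading A for a patient who leaves without attending the final visit. Both readings are open, and neither removes the gap for every patient.

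**The two periods need not match.** A reader might infer that the protocol contradicts itself. It does not: one rule governs conception and the other notification, and nothing requires equal lengths. The only explanation offered for 75 days is the spermatogenic cycle, given for men. Section 9.5.2 does not forbid later reports either. The point is therefore an improvement to a stated rule, not an outright error.

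**The risk is low.** This stands in full. In rats "there were no effects on mating, fertility, ovarian or uterine parameters, or fetal development despite reductions (-88% from baseline) in serum vitamin A", and the primate work included "a chronic NHP study in sexually mature animals, where there were no adverse effects in males (including sperm analyses and spermatogenic staging) or females". Section 1.4 adds that "the lowering of circulating vitamin A associated with suppression of RBP does not result in severe vitamin A deficiency". Pre-dose testing makes it unlikely that an established pregnancy is dosed at the final infusion. A reader might infer from Section 1.2, where TTR in healthy volunteers was recovering at Day 28 and back to baseline by Day 70, that the uncovered days are days of active drug effect. Some may precede full recovery, but the documents do not show how many, or that any harm follows.

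**Conclusion.** The point holds as a low-severity improvement in safety follow-up. Section 9.5.2 leaves about 40–45 of the 75 post-dose days (53–60%) without a clear duty to report or follow a female patient's pregnancy if the course of the study means her own participation. If it means the whole trial, the shortfall is confined to patients whose last dose falls near study close. On either reading, a pregnancy conceived inside the window but recognised after it closes can be missed.

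The conclusion assumes a month of 30 or 31 days and a final visit no later than day 35. It applies to the Brazil version 3.1 text, with the same reporting sentence in Argentina version 3.1. The integrated global text is not in the part available. The Amendment 2 change summaries that are shown list no change to Section 9.5.2, so the wording probably carries over, but that is an inference.

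A reader might take the yield figures as a ceiling on missed pregnancies. They are not one. What can be said is that the expected number is very small and that no trial result changes.

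**What to change.** Amend Section 9.5.2 so that the investigator reports, and follows to outcome, any pregnancy in a female patient that is found during her participation or within 75 days after her last dose, or that is known to have been conceived in that period. This aligns reporting with the contraception period, covers late recognition, and removes the dependence on how the course of the study is read. Make the same change in Argentina version 3.1 and in any other version that carries the sentence.

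As an optional clarification, give partner pregnancies a stated end date too.

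The cost is one clause and about six more weeks (40–45 days) of passive reporting by sites for each departing patient. No visit or test is added.
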